3.3.2 Dose Adjustment of tofacitinib

Tofacitinib dose should be reduced for infection, hepatic impairment, myelosuppression or other events as per package insert. Dose modifications will be based on the package insert recommendations for ulcerative colitis and should be followed for renal impairment, hepatic impairment, lymphopenia, neutropenia, anemia, and in patients taking strong or moderate CYP3A4 inhibitors (as can be found here: Flockhart Table or in another frequently updated source).

If VTE prophylaxis medication is missed or held for more than 3 days (e.g. in case of renal impairment or procedure like tumor biopsy), then tofacitinib should be held until anticoagulation can be restarted.

3.3.3 Schedule Modifications When Study Drugs must be Held

If a patient begins treatment with tofacitinib but is unable to receive any planned dose of LMB-100 on schedule due to medical or other complications unrelated to tofacitinib treatment:

- For delays in LMB-100 administration anticipated to be ≤ 48 hrs, tofacitinib should be continued. LMB-100 administration should resume within the 48-hour window. Tofacitinib treatment should be extended so that patients continue to receive tofacitinib treatment for two days beyond the last LMB-100 infusion
- For delays lasting or anticipated to last >48hrs, tofacitinib treatment should be stopped.

When tofacitinib is stopped mid-cycle due to medical or other complications related or unrelated to tofacitinib:

• If any LMB-100 was administered, the remaining doses of LMB-100 may be given with or without restart of tofacitinib, per investigator's discretion. If tofacitinib is restarted, it should be continued for two days beyond the last LMB-100 infusion

If no LMB-100 was administered, the cycle is aborted. Patients have 4 weeks from the date of the last tofacitinib dose to restart (from Day 1) the planned schedule for the cycle. No more than 2 cycles may be aborted and restarted. If Cycle 1 treatment is aborted and baseline imaging studies to assess tumor burden (CT CAP or other) were performed >28 days before cycle restart, then baseline imaging studies should be repeated prior to first LMB-100 dose of the restarted cycle. Baseline tumor biopsy should not be repeated.

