1.2.7 Rationale for starting dose and schedule of tofacitinib

Tofacitinib is FDA approved for the treatment of ulcerative colitis at a dose of 10 mg (immediate release formulation) given orally twice daily on a continuous schedule. Tofacitinib will be given at the same dose on this protocol, which is the highest dosage approved by FDA for any indication. For our purpose- diminishing ADA formation- we anticipate that immunosuppression by tofacitinib will only be necessary during the time which immune cells are potentially exposed to LMB-100. Therefore, tofacitinib will not be given continuously. Instead, dosing will be limited to days 1 through 10 of each cycle. This provides immunosuppression throughout the three doses of LMB-100, a lead-in for 3 days before to establish physiologic effect before the first LMB-100 administration, and then continued tofacitinib for 2 days after last administration of LMB-100 for the cycle while the drug is eliminated from the body. Intermittent dosing is anticipated to reduce the risk of infection caused by tofacitinib-mediated immune suppression and hypothetical risk of inhibiting anti-tumor immune response.

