3.2.3 Schematic view of the administration set-up

3.3 DOSE MODIFICATIONS

3.3.1 LMB-100

LMB-100 infusion may be held for up to 48 hours due to drug-associated toxicity or adverse events from other intercurrent medical conditions (such as primary cancer diagnosis) that resolve with or without medical intervention to grade 1 or less within this time frame. Toxicities for which further LMB-100 treatment should NOT be given are stated below in **Table 12**, which also provides guideline on how to manage some toxicities anticipated with LMB-100.

Event	Action to Be Taken
IRR/hypersensitivity reaction during administration of LMB-100	If an IRR/hypersensitivity develops, the infusion of LMB-100 should be temporarily interrupted. The participant should be monitored until complete resolution of the symptoms and treated as clinically indicated. Treatment or concomitant medication may include IV saline, oxygen, bronchodilators, corticosteroids, and vasopressors depending on the symptoms.
	 If the infusion is interrupted: In the event of IRR CTCAE Grade1, upon resolution of symptoms, the infusion will resume at the rate being used at the time that the IRR occurred In the event of IRR Grade 2 or 3, upon resolution of symptoms, the infusion will resume at one-half the previous rate. In the event of IRR CTCAE Grade 3 or Grade 4 (which may include pulmonary or cardiac events) or an anaphylactic reaction, the infusion should not be restarted, and the participant should receive aggressive treatment Participants experiencing IRR CTCAE Grade 4 or anaphylaxis must be permanently discontinued from study treatment For participants receiving LMB-100 who previously experienced IRR CTCAE ≥ Grade 2, the infusion rate for subsequent LMB-100 infusion should be reduced to one-half of the previous rate and corticosteroids premedication should be given 30 minutes prior to infusion in addition to standard pre-medications: Dexamethasone (20 mg PO 6 -12hrs before infusion or 8
	mg IV, $30 - 90$ min before infusion) or equivalent dose of another corticosteroid as clinically indicated
Capillary leak syndrome (CLS)	In the event of Grade 4 CTCAE capillary leak syndrome (urgent intervention indicated):

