Renal toxicity	In the event of Grade 1 or greater renal toxicity consider increasing oral or intravenous hydration, and consider delaying LMB-100 administration by up to 48hrs.			
	In the event of Grade 2 or greater renal toxicity hold LMB-100 administration until recovery to Grade 1 or better. If this does not occur within 48hrs, no further LMB-100 should be given during the cycle.			
IRR = infusion related reaction; IV =	= intravenous; CTCAE = Common Terminology Criteria for Adverse			

Events

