12.1.2 Toxicity

Information in this section is based on preclinical studies with LMB-100, and clinical studies of the cytolytic fusion protein SS1-P. Participants should receive a full dose of LMB-100 unless a DLT and/or a treatment limiting toxicity is observed. In case of DLT and/or treatment limiting toxicities, treatment with LMB-100 will be stopped until resolution of toxicity to NCI CTCAE Grade ≤ 2 hematological toxicities or Grade ≤ 1 non-hematological toxicities. A delay of LMB-100 administration for up to two weeks of the planned schedule will be acceptable to allow for resolution of toxicities. If toxicity does not resolve to NCI CTCAE Grade ≤ 2 hematological toxicities. If toxicity does not resolve to NCI CTCAE Grade ≤ 2 hematological toxicities or Grade ≤ 1 non-hematological toxicities and the participant is unable to resume treatment with LMB-100 after this time, no additional doses will be administered, and the participant will be withdrawn from study treatment.

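### Sections 3.3.1 and 3.3.3 disagree on LMB-100 after a hold of more than 48 hours, and the expansion analysis has no breakdown by tofacitinib cover

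*Combined protocol and SAP*

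**What the plan says.** **Hold rules**

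- Section 3.3.1: "LMB-100 infusion may be held for up to 48 hours due to drug-associated toxicity or adverse events from other intercurrent medical conditions", provided the event falls to grade 1 or lower in that time. For grade 2 or greater renal toxicity, Table 12 holds LMB-100 until grade 1 or better and adds: "If this does not occur within 48hrs, no further LMB-100 should be given during the cycle".
- Section 3.3.3, first part (an infusion is late for a reason unrelated to tofacitinib): for delays of 48 hours or less, tofacitinib continues and "LMB-100 administration should resume within the 48-hour window". Otherwise: "For delays lasting or anticipated to last >48hrs, tofacitinib treatment should be stopped".
- Section 3.3.3, second part (tofacitinib stopped mid-cycle for any reason): "If any LMB-100 was administered, the remaining doses of LMB-100 may be given with or without restart of tofacitinib, per investigator's discretion". There is no time limit and no pointer to 3.3.1.
- Section 12.1.2, after a DLT or treatment-limiting toxicity: "A delay of LMB-100 administration for up to two weeks of the planned schedule will be acceptable to allow for resolution of toxicities". Recovery means grade 2 or lower for hematological toxicity and grade 1 or lower for other toxicity. A patient who does not recover in that time is withdrawn from study treatment.
- Section 3.4 separately allows a cycle to start up to two weeks late because of toxicity.

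**Planned cover.** Section 1.2.7 explains the day 1 to 10 tofacitinib schedule: "This provides immunosuppression throughout the three doses of LMB-100, a lead-in for 3 days before to establish physiologic effect", followed by two more days after the last infusion.

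**Analysis.** The expansion endpoint (10.1.1) is a level above 600 ng/mL at the end of any cycle 2 infusion. A patient is evaluable if cycle 2 drug levels can be assessed (10.3.1). Success is 11 or more of 15 (10.2). None of 10.1.1, 10.2, 10.3.1 or 10.4.2 mentions tofacitinib exposure. By contrast, DLT evaluability in 10.3.1 requires every dose of study drugs unless a DLT occurs.

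**The concern.** There are two separate problems.

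The first is a safety rule that reads two ways. Once a hold passes 48 hours, the answer to whether the rest of that cycle's LMB-100 may be given depends on the section consulted.

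The second is interpretation. The expansion phase asks whether co-administered tofacitinib delays neutralizing antibodies through cycle 2. Section 3.3.3 lets a patient receive some infusions after tofacitinib has stopped. That patient still counts in the 11-of-15 decision, and no planned table would show how many such patients there were or how they fared. If the result falls just short of 11, a reader could not separate failure of the combination from incomplete delivery of it.

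**Working it through.** **1. The hold rules side by side**

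Take a patient who has the day 4 infusion and then a grade 2 creatinine rise that has not recovered after 48 hours.

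| Section | LMB-100 for the rest of the cycle | Tofacitinib |
|---|---|---|
| 3.3.1 and Table 12 | None | Not addressed |
| 3.3.3 | Remaining doses allowed, no time limit | Stopped; restart optional |
| 12.1.2 (if the event is a DLT or treatment-limiting) | Delay of up to two weeks, then withdrawal if unresolved | Not addressed |

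The first two rows conflict directly. The third depends on how the two weeks is read. Moving the infusion days:

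- 48 hours: days 4, 6, 8 become 6, 8, 10.
- Two weeks: days 4, 6, 8 become 18, 20, 22. Day 22 lies outside a 21-day cycle.

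This favors a between-cycle reading of 12.1.2, as does its match with the two-week cycle delay in 3.4 and the cycle 2 start rule in 3.1.1. Its wording does not say so, however. The recovery grade for hematological toxicity (2 or lower in 12.1.2, 1 or lower in 3.3.1) differs on either reading.

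**2. Routes to an uncovered infusion**

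A long LMB-100 hold is one route. Another needs no LMB-100 hold: section 3.3.2 holds tofacitinib when VTE prophylaxis is missed or held for more than 3 days, and 3.3.3 could then let LMB-100 continue alone. The 48-hour cap does not close that route.

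**3. The plan's own figures**

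Inputs from 10.2: n = 15, success at 11 or more, rates 50% and 80%.

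P(X ≥ 11) = Σ C(15,x) p^x (1−p)^(15−x), x = 11 to 15.

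- p = 0.5: (1365 + 455 + 105 + 15 + 1)/32768 = 1941/32768 = 0.0592. The plan states 5.9%.
- p = 0.8: 0.8358. The plan states 83.6%.

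Both reproduce.

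**4. Worst-case dilution**

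Assumption: k of the 15 had uncovered doses and revert fully to 50%, while the rest are at 80%. The 50% is close to the historical cycle 2 rate without tofacitinib in Table 6 (19/39 = 49%). The documents do not give k.

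X = Binomial(15−k, 0.8) + Binomial(k, 0.5). For k = 1: 0.5 × P(Bin(14, 0.8) ≥ 11) + 0.5 × P(Bin(14, 0.8) ≥ 10) = 0.5 × 0.6982 + 0.5 × 0.8702 = 0.7842.

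| k | Expected rate | P(X ≥ 11) |
|---|---|---|
| 0 | 80% | 83.6% |
| 1 | 78% | 78.4% |
| 2 | 76% | 72.4% |
| 3 | 74% | 65.8% |
| 4 | 72% | 58.7% |
| 5 | 70% | 51.4% |

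If tofacitinib has no effect, covered and uncovered patients are all at 50%, so X is Binomial(15, 0.5) and the type I error is 5.9% for every k.

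**The case against.** The best defense is that the sections can be read together. Section 3.3.1 presents Table 12 as listing when LMB-100 must not continue, and a specific prohibition normally outranks a general permission. The sentence in 3.3.3 may only be answering whether tofacitinib has to be restarted. It also covers tofacitinib stopped for its own toxicity, where no LMB-100 hold arises. Treatment is given at one center, and the team discusses each patient weekly (7.4.1), which limits inconsistent application. This lowers the practical risk, but 3.3.3 still addresses delays beyond 48 hours, sets no end to them and nowhere defers to 3.3.1. The precedence has to be supplied by the reader.

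Three stronger readings are tempting and not supported:

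- *That 12.1.2 is a third, incompatible within-cycle limit.* It can be read in sequence with 3.3.1: stop for the cycle, delay the next, then withdraw. For a creatinine rise its recovery grade is the same as in 3.3.1. What stands is the unstated scope and the hematological mismatch.
- *That 3.3.3 contradicts 1.2.7.* Section 1.2.7 explains the planned schedule, while 3.3.3 handles departures from it.
- *That affected patients were immunized without tofacitinib.* The clause applies only after tofacitinib was begun and at least one infusion given, so cover was partial. Full reversion to 50% is therefore an upper bound chosen for illustration. Moreover, any cycle 2 infusion can meet the endpoint, so a qualifying level reached before tofacitinib stopped in cycle 2 is not undone. The exposure that matters most is in cycle 1.

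**Conclusion.** The point holds and should be fixed. For a hold beyond 48 hours, 3.3.1 with Table 12 and 3.3.3 give different answers, and 12.1.2 leaves its scope open. Separately, the plan counts patients with uncovered infusions without stating that this is intended and without showing them.

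The size of the statistical effect is unknown. A reader might scale up the 2 of 13 creatinine increases in Table 4 to about 2 of 15 here. The table does not support that: both events were at 250 mcg/kg, with none in the 1 + 1 + 3 + 4 = 9 patients at 45 to 170 mcg/kg, and this trial's highest level is 140. Table 4 also gives no duration. Sections 1.2.8.2.1 and 1.2.8.2.3 make renal holds foreseeable but give no rate for holds over 48 hours.

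A reader might also infer that a positive result becomes less credible. It does not: if tofacitinib works, the effect is dilution, at most about 5 to 7 percentage points of power per affected patient in the illustration for one to three patients. The type I error is unchanged. Counting every evaluable patient is a legitimate choice, but the plan needs to state it.

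**What to change.** **Protocol text.** The sponsor should reconcile 3.3.1 with Table 12, 3.3.3, 3.4 and 12.1.2. The text should separate a hold within a cycle from a delay between cycles, align or explain the recovery grades, and say which section governs LMB-100 once tofacitinib has stopped. No clinical rule is proposed here.

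**Section 10.4.2.** State that all evaluable patients stay in the 11-of-15 count, whatever their tofacitinib cover. Add one pre-specified supportive tabulation: the cycle 2 fraction, with numerator and denominator, among patients whose every LMB-100 infusion up to the qualifying sample was covered by tofacitinib. For patients who never exceed 600 ng/mL, use the last cycle 2 end-of-infusion sample. The section should define what counts as covered. The dosing records and the tofacitinib diary (3.2.1, Appendix C) supply the data.

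**Cost.** Wording and one table, with no new patients or samples. The added denominator is smaller and selected on events after treatment began. Patients who qualify early also have less time to lose cover, which tends to favor successes. The table can help in reading the primary result but cannot replace it.

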3.4 STUDY CALENDAR

Unless otherwise specified, screening assessments must occur within 28 days prior to registration for study treatment. Cycle 1, day 1 assessments may occur up to 7 days prior to treatment initiation. If screening tests were performed within this window, then they do not need to be repeated on C1D1. Dosing cycles may be delayed for up to one week or started up to 2 days early to accommodate schedule conflicts, federal holidays and inclement weather, etc. They may be delayed for up to two weeks due to toxicity. There is no time limit on dosing cycle delays for patients receiving treatment extension.

			All Cycl	es (21 da	ys)					Post T	herapy
Procedure	Screening	Day 1	Day 3*	Day 4	Day 6	Day 8	Day 9	Day 15	Day 21	Safety Follow Up Visit ⁷	Long Term Follow Up ¹¹
Tofacitinib		ad	ministered	BID days	1-10 of ea	ach cycle					
Prophylactic anti- coagulation		Khorana Score < 2: administer daily on days 1-11 of each cycle Khorana Score ≥ 2: administer throughout treatment until 14 days after last dose of tofacitinib/ LMB-100									
LMB-100				Х	Х	Х					
History and PE	Х	C1 only	Х		Х	Х				Х	
Weight			Х		Х	Х	C1 only			Х	
Height			C1 only								
Vital signs ¹	Х	C1 only	Х	Х	Х	Х	C1 only			Х	
ECOG Performance Status	X	C1 only	X							Х	
Labs ²	X	C1 only	X		Х	Х		C1 only ¹⁴	C1 only ¹⁴	Х	
D-dimer		C1 only	Х			Х					
Cholesterol Panel		C1 only								Х	
TBNK		C1 only	C1 and C3 only				C1 only				
1,25-dihydroxy Vit D	Х									Х	

Abbreviated Title: LMB100 + *tofacitinib in PDA Version Date:* 08/19/20

			All Cycl	es (21 da	ys)					Post T	herapy
Procedure	Screening	Day 1	Day 3*	Day 4	Day 6	Day 8	Day 9	Day 15	Day 21	Safety Follow Up Visit ⁷	Long Term Follow Up ¹¹
Hepatitis and HIV screening panel	Х										
IGRA	Х										
Urinalysis	Х		Х		Х	Х				Х	
Urine albumin and creatinine	C1 only		C1 only		C1 only	C1 only					
Pregnancy test ³	Х		Х								
Confirmation of Dx ⁴	Х										
Assessment of tumor MSLN expression ^{4, 5}	X										
CT CAP and/or MRI ⁸	X	•	cles of stud	•		days				Х	Х
CA 19-9-or appropriate tumor-specific marker ⁵			Х							X	
Doppler U/S of bilateral lower extremities		Optional ¹⁵									
ECG	X		C1 only			C1 only				X	
Echocardiogram	Х										
Ambulatory Oxygen Saturation	Х										
Chest X-ray			X ⁹								
NIH Advance Directives Form ⁶		C1 only ⁶									
Biopsy	X ¹³	C1 only ¹²	C2 only 12								

Abbreviated Title: LMB100 + tofacitinib in PDA *Version Date:* 08/19/20

			All Cycl	es (21 da	ys)					Post T	herapy
Procedure	Screening	Day 1	Day 3*	Day 4	Day 6	Day 8	Day 9	Day 15	Day 21	Safety Follow Up Visit ⁷	Long Term Follow Up ¹¹
PKs		Please refer to Section 5.2									
Correlative Studies		Please	refer to Sec	ction 5.2							
Annual phone call to monitor survival and additional CA therapy											Х
Adverse events ¹⁰		Monitored continuously									
Concomitant meds		Monitored continuously									

*If not performed on day 3, may be performed on day 4 prior to the start of LMB-100 infusion

- Vital signs including temperature, blood pressure, pulse rate, and oxygen saturation should be recorded on the indicated days. In addition, systolic blood pressure, pulse rate, and oxygen saturation must be monitored pre-infusion, every 15 minutes (± 5 minutes) during the infusion, at end of infusion (EOI), then 30, 60 and 120 minutes (±15 minutes) following EOI.
- ² CBC with differential, Acute Care Panel, Hepatic Panel, Mineral Panel, C-reactive protein (CRP), Creatine Kinase (CK), PT, PTT, LDH. PT and PTT will be done only at the time of screening, Day 1 of each cycle, and within 24hrs prior to biopsies (if biopsy will be performed).
- ³ Pregnancy test required in women of childbearing potential; i.e. premenopausal women and women ≤ 2 years after menopause (menopause is defined as amenorrhea for > 2 years)
- ⁴ Assessment may occur at any time prior to enrollment
- ⁵ Applicable only to patients on dose escalation with tumor types other than pancreatic adenocarcinoma, extrahepatic cholangiocarcinoma, or epithelioid subtype of mesothelioma
- ⁶ As indicated in Section **11.3**, all subjects will be offered the opportunity to complete an NIH advanced directives form. This should be done preferably prior to beginning treatment but can be done at any time during the study as long as the capacity to do so is retained. The completion of the form is strongly recommended but is not required.
- ⁷ Safety follow up will occur 3 6 weeks after last dose of study therapy. If the patient is unable to return to the clinic for the follow up visit, an adverse event assessment will be performed by telephone.

- ⁸ Scans, every ~9 weeks, will only be performed until disease progression. Note: for patients on long term follow up, scans may be performed outside of NIH. Gadolinium will be used for MRI in patients where MRI is required.
- ⁹ Chest x-ray on cycle 1 only for patients with existing mediport. Chest x-ray is required with each cycle to confirm placement of a central line if placement is required for drug administration.
- ¹⁰ Adverse events will be monitored continuously for 30 days beyond the last treatment.
- Study visits after safety follow up visit will be encouraged but not required. Only patients who are removed from study therapy for reasons other than disease progression will be invited to return to clinic (approximately every 6 weeks) for the indicated scans and labs until disease progression. All patients will be followed until death through phone contact for overall survival.
- ¹² Optional at cycle 1 day 1 and cycle 2 day 3.
- ¹³ Only if archival tumor tissue is not available
- ¹⁴ +/- 1 day
- ¹⁵ Should not be performed in patients on daily systemic anticoagulation prior to study enrollment / start. May be performed up to 14 days before or 3 days after cycle 1 day 1.

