2 ELIGIBILITY ASSESSMENT AND ENROLLMENT

2.1 ELIGIBILITY CRITERIA

2.1.1 Inclusion Criteria

- 2.1.1.1 Patients must have histologically confirmed solid tumor malignancy for which no curative therapy exists.
- 2.1.1.2 Pancreatic adenocarcinoma, extrahepatic cholangiocarcinoma or epithelioid subtype of mesothelioma, as determined by NCI Laboratory of Pathology, OR for all other tumor types, at least 20% of tumor cells must express mesothelin. Determination can be made using archival tumor tissue or fresh biopsy if archival tumor tissue is not available.
- 2.1.1.3 All patients must have evaluable disease (i.e. measurable per RECIST 1.1. or by following CA19-9 tumor marker). Patients in the expansion cohort must have measurable disease, per RECIST 1.1. See Section 6.3 for the evaluation of measurable disease.
- 2.1.1.4 Patients must have received at least one prior standard systemic treatment regimen for advanced disease OR be ineligible to receive available standards due to co-morbidities, prior toxicity, lack of standard options for tumor type, or having received all standards

available for prior treatment of early stage disease OR have refused first-line standard systemic treatment but have received prior anti-cancer treatments.

- 2.1.1.5 Patients with dMMR/MSI-H disease must have received at least one prior anti-PD1 therapy, be ineligible to receive this treatment due to concurrent medical conditions, or have refused this therapy.
- 2.1.1.6 ECOG performance status (PS) 0-2 (Appendix A- Performance Status Criteria).
- 2.1.1.7 Age ≥18 years. Because no dosing or adverse event data are currently available on the use of LMB-100 alone or in combination with tofacitinib in persons with <18 years of age, children are excluded from this study.
- 2.1.1.8 Patients must be more than 14 days removed from most recent minor surgical procedure (such as biliary stenting), 28 days from most recent major surgical procedure and 14 days from radiation therapy, systemic treatments (such as chemotherapy), or experimental drug treatment. All acute toxicities from prior treatment must have resolved to grade 1 or less except alopecia, anemia, peripheral neuropathy, or endocrinopathies corrected by replacement therapy.
- 2.1.1.9 Adequate hematological function: neutrophil count of $\ge 1.5 \times 10^3$ cells/µL, platelet count of $\ge 85,000/\mu$ L, hemoglobin ≥ 9 g/dL
- 2.1.1.10 Serum albumin \geq 2.5 mg/dL without intravenous supplementation

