2.2.2 Screening activities performed after a consent for screening has been signed

For patients requiring testing for MSLN expression (see Section 2.3.1), screening will occur on this study. For all other subjects, screening will occur on study 01-C-0129.

The following activities will be performed only after the subject has signed the appropriate consent for screening. They will be performed within 28 days before registration for study treatment unless specified:

- Assess tumor MSLN expression by immunohistochemistry analysis in archival tissue or fresh biopsy samples ONLY for patients who do not have a diagnosis of epithelioid mesothelioma, extrahepatic cholangiocarcinoma or pancreatic adenocarcinoma.
- Medical History and physical exam
- Vital signs including ambulatory oxygen saturation by pulse oximetry
- ECOG performance status
- Pregnancy test in women of childbearing potential (within 7-days prior to initiation of study therapy)
- ECG
- Echocardiogram
- CT scan of chest, abdomen and/or pelvis and areas of known or suspected disease involvement; MRI and/ or PET scan may also be performed when appropriate per PI discretion.
- CBC with differential, Acute Care Panel (sodium, potassium, chloride, bicarbonate, creatinine, glucose, BUN), Hepatic Panel (alkaline phosphatase, AST, ALT, total bilirubin, direct bilirubin), Mineral Panel (albumin, calcium, magnesium, phosphorus), creatine kinase, C-reactive protein, 1,25-dihydroxy vitamin D, Coagulation (PT, PTT), lactate dehydrogenase
- CA 19-9 serum tumor marker for pancreatobiliary cancer patients, or other appropriate tumor marker in other tumor types
- Testing for HIV, HCV, HBV: anti-HIV antibody, Anti-HCV Antibody, HBs Ag Screening
- Screening for latent tuberculosis by interferon-x release assay: QuantiFERON-TB Gold Plus or similar
- Urinalysis

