6 DATA COLLECTION AND EVALUATION

6.1 DATA COLLECTION

The PI will be responsible for overseeing entry of data into an in-house password protected electronic system (C3D and Labmatrix databases) and ensuring data accuracy, consistency and timeliness. The principal investigator, associate investigators/research nurses and/or a contracted data manager will assist with the data management efforts. All data obtained during the conduct of the protocol will be kept in secure network drives or in approved alternative sites that comply with NIH security standards. Primary and final analyzed data will have identifiers so that research data can be attributed to an individual human subject participant.

All adverse events, including clinically significant abnormal findings on laboratory evaluations, regardless of severity, will be followed until return to baseline or stabilization of event.

Document AEs from the first study intervention, Study Day 1, through the end of the treatment. After 30 days, only adverse events which are serious and related to the study intervention need to be recorded.

An abnormal laboratory value will be recorded in the database as an AE **only** if the laboratory abnormality is characterized by any of the following:

- Results in discontinuation from the study
- Is associated with clinical signs or symptoms
- Requires treatment or any other therapeutic intervention
- Is associated with death or another serious adverse event, including hospitalization.
- Is judged by the Investigator to be of significant clinical impact

• If any abnormal laboratory result is considered clinically significant, the investigator will provide details about the action taken with respect to the test drug and about the patient's outcome.

End of study procedures: Data will be stored according to HHS, FDA regulations, and NIH Intramural Records Retention Schedule as applicable.

Loss or destruction of data: Should we become aware that a major breach in our plan to protect subject confidentiality and trial data has occurred, this will be reported expeditiously per requirements in Section 7.2.1.

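### From cycle 2 onward the only scheduled pregnancy test comes after 4 to 7 of the cycle's 20 tofacitinib doses; a test shortly before the first dose would close the gap cheaply

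*Combined protocol and SAP*

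**What the plan says.** Sections 3.1.2 and 3.2.1 give tofacitinib twice daily on Days 1-10 of each 21-day cycle, self-administered when the patient is at home. LMB-100 follows on Days 4, 6 and 8.

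**Pregnancy test.** For entry, 2.2.2 lists "Pregnancy test in women of childbearing potential (within 7-days prior to initiation of study therapy". In the 3.4 calendar the row is filled at screening and on Day 3, and the Day 1 cell is empty. The Day 3 column carries the footnote "If not performed on day 3, may be performed on day 4 prior to the start of LMB-100 infusion". Footnote 3 defines the women concerned as "premenopausal women and women ≤ 2 years after menopause". Exclusion 2.1.2.13 rests on unknown fetal effects of LMB-100, tofacitinib or both.

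**Laboratory panel.** The Labs row (blood count, chemistry and hepatic panel among others) is filled on Days 3, 6 and 8 of every cycle. Days 1, 15 and 21 are marked for cycle 1 only. Footnote 2 names PT and PTT on Day 1 of each cycle, which does not match that row. Section 3.3.2 bases tofacitinib adjustment on renal and hepatic impairment and on blood counts.

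**Timing of later cycles.** Section 3.4 states "Dosing cycles may be delayed for up to one week or started up to 2 days early to accommodate schedule conflicts", adds "They may be delayed for up to two weeks due to toxicity", and for extension says "There is no time limit on dosing cycle delays for patients receiving treatment extension". Under 3.1.3, extension monitoring follows the same calendar.

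**The concern.** The Day 3/4 test is well placed to prevent LMB-100 exposure in pregnancy. It cannot do the same for tofacitinib, which has already restarted, although the exclusion criterion names both drugs. The plan's own entry standard is a test before any study therapy, and that standard lapses after cycle 1. A woman who follows the calendar exactly can take several tofacitinib doses before an early pregnancy is looked for.

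The same pattern appears, less importantly, for laboratory values. From cycle 3, nothing scheduled between the previous Day 8 and the new Day 1 would show a silent renal, hepatic or blood-count change. The Day 8 panel is drawn on the day of the third LMB-100 infusion, so it cannot show that infusion's later effect. Section 12.1.2.5 lists increased creatinine as a risk of LMB-100.

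**Working it through.** The plan states no figure on this point, so there is none to reproduce. The check is a count of doses and days.

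**Inputs.** Two doses a day for 10 days (3.1.2); 21-day cycle with LMB-100 on Days 4, 6 and 8 (3.2.2); pregnancy test on Day 3, or Day 4 before LMB-100 (3.4); last scheduled panel on Day 8 in cycles 2 and later (3.4); cycle shift of -2 to +7 days for scheduling and up to +14 days for toxicity (3.4).

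**Doses before the test.** Total per cycle: 2 × 10 = 20. Doses before the test = 2 × completed days + doses already taken that day.

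| Time of test | Doses before | Share of 20 | Doses remaining |
|---|---|---|---|
| Day 3, before morning dose | 2 × 2 = 4 | 20% | 16 |
| Day 3, after morning dose | 4 + 1 = 5 | 25% | 15 |
| Day 3, after evening dose | 4 + 2 = 6 | 30% | 14 |
| Day 4, before morning dose | 2 × 3 = 6 | 30% | 14 |
| Day 4, after morning dose | 6 + 1 = 7 | 35% | 13 |

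**Age of the last scheduled test or panel at the next first dose.** The next Day 1 falls on Day 22 + shift of the current cycle. Age = (22 + shift) - day of test.

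| Start of next cycle | Pregnancy test (Day 3 / Day 4) | Day 8 panel |
|---|---|---|
| 2 days early (Day 20) | 17 / 16 days | 12 days |
| On schedule (Day 22) | 19 / 18 days | 14 days |
| One week late (Day 29) | 26 / 25 days | 21 days |
| Two weeks late, toxicity (Day 36) | 33 / 32 days | 28 days |

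The pregnancy column applies from cycle 2, the panel column from cycle 3. Cycle 2 differs for laboratory values because of the cycle 1 Day 21 (± 1) panel. That panel is 0-2 days old on schedule, 7-9 days after a one-week delay and 14-16 days after a two-week delay. All ages refer to scheduled tests only.

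**How many patients.** Section 10.2 plans for up to 27 evaluable patients (12 + 15) under an accrual ceiling of 45, which also covers screen failures and patients who do not complete the DLT period. The share of women of childbearing potential is not given. Assuming 5-15%:

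- Of 27: 27 × 0.05 = 1.4 to 27 × 0.15 = 4.1, or about 1-4 women.
- Of 45: 45 × 0.05 = 2.3 to 45 × 0.15 = 6.8, or about 2-7 women, an upper figure because screen failures are included.

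Each would meet the gap at up to two planned cycle starts (cycles 2 and 3), plus any extension cycles.

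**The case against.** Several safeguards already stand. Contraception and immediate reporting of a suspected pregnancy are required (2.1.1.16), and a pregnancy stops treatment (3.5, 8.4.1). Women are tested about every three weeks and always before LMB-100, with 13 to 16 tofacitinib doses still to come. These points keep the risk small. They do not put a test before tofacitinib.

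The laboratory part draws a stronger defence, and most of it holds. Fewer panels after cycle 1 is an ordinary staged choice: cycle 1 has the Day 15 and Day 21 draws, and Days 3/4, 6 and 8 remain in every cycle. A panel before every Day 1 would mean an off-site draw and a result review for every patient, because tofacitinib can be started at home.

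Four stronger readings are tempting, and the documents do not support them.

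- *That a patient delayed for toxicity goes 28 days without blood work.* Section 6.1 says adverse events, including clinically significant laboratory findings, "regardless of severity, will be followed until return to baseline or stabilization of event". Section 12.1.2 requires a DLT or treatment-limiting toxicity to resolve to a stated grade before LMB-100 resumes. A laboratory toxicity that causes the delay would therefore be rechecked. The 28 days applies only if no unscheduled labs are drawn.
- *That renal and hepatic values go unchecked without limit in extension.* After a deferral beyond 6 weeks or an intervening therapy, 3.1.3 applies the blood-count and albumin criteria and 2.1.1.8 ("All acute toxicities from prior treatment must have resolved to grade 1 or less"). It also lets the investigator repeat screening safety evaluations, which include chemistry, hepatic and pregnancy tests. What remains is that no renal or hepatic panel, and no pregnancy test, is mandated.
- *That the tofacitinib dose rules in 3.3.2 fail.* The Day 3/4 panel still allows adjustment within the cycle.
- *That at most 27 patients can be affected.* That number counts evaluable patients; the accrual ceiling is 45.

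**Conclusion.** The pregnancy-test gap is real and follows directly from the calendar. From cycle 2, including extension, 4 to 7 of 20 tofacitinib doses precede the only scheduled test, against the plan's own exclusion criterion and entry standard. It probably concerns a handful of women, but that count rests on an assumed 5-15% share, and the documents give no likelihood of harm. The laboratory point is secondary and optional: the newest scheduled panel at restart from cycle 3 is 14 days old on schedule, 21 after a one-week delay, and up to 28 after a two-week delay with no unscheduled labs. No endpoint, sample size or dose-escalation rule is affected. This is a minor, cheap safety improvement.

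**What to change.** **Main change.** For every cycle from 2 onward, including extension, require a negative pregnancy test in women of childbearing potential (footnote 3) shortly before the first tofacitinib dose. The window could be 3 days or the plan's own 7 days; the choice is a judgement. A local or urine test is acceptable. Keep the Day 3/4 test before LMB-100. No tofacitinib dose of the cycle would then precede its first test. The cost is a calendar amendment and one inexpensive extra test per later cycle for a few women.

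**Optional.** Where feasible, obtain and review a local blood count, chemistry and hepatic panel before tofacitinib restarts from cycle 3. At minimum, do so after a delayed start or an extension deferral. Footnote 2 already names a Day 1 PT/PTT draw in each cycle, to which these tubes could be added if results are reviewed before the first dose; the amendment should also reconcile that footnote with the Labs row. The cost is a possible off-site draw and a result review per later cycle, which is why this part is a suggestion.
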